## 6.3.4. Cardiovascular Events

Investigators will be required to fill out event specific data collection tools for the following AEs and SAEs:

- Myocardial infarction/unstable angina
- Congestive heart failure
- Arrhythmias
- Valvulopathy
- Pulmonary hypertension
- Cerebrovascular events/stroke and transient ischemic attack
- Peripheral arterial thromboembolism
- Deep venous thrombosis/pulmonary embolism
- Revascularisation

This information should be recorded in the specific cardiovascular eCRF within one week of when the AE/SAE(s) are first reported.

### 6.3.5. Death Events

In addition, all deaths will require a specific death data collection tool to be completed. The death data collection tool includes questions regarding cardiovascular (including sudden cardiac death) and noncardiovascular death.

This information should be recorded in the specific death eCRF within one week of when the death is first reported.

#### 6.3.6. Pregnancy

Any pregnancy that occurs during study participation must be reported using a clinical trial pregnancy form. To ensure subject safety, each pregnancy must be reported to GSK within 2 weeks of learning of its occurrence. The pregnancy must be followed up to determine outcome (including premature termination) and status of mother and child. Pregnancy complications and elective terminations for medical reasons must be reported as an AE or SAE.

Any SAE occurring in association with a pregnancy, brought to the investigator's attention after the subject has completed the study and considered by the investigator as possibly related to the study treatment, must be promptly reported to GSK.

In addition, the investigator must attempt to collect pregnancy information on any female partners of male study subjects who become pregnant while the subject is enrolled in the study. Pregnancy information must be reported to GSK as described above.

### 6.3.7. Time Period and Frequency of Detecting AEs and SAEs

The investigator or site staff is responsible for detecting, documenting and reporting events that meet the definition of an AE or SAE.

AEs will be collected from the start of study treatment and until the follow up contact.

SAEs will be collected over the same time period as stated above for AEs. However, any SAEs assessed as related to study participation (e.g., study treatment, protocol-mandated procedures, invasive tests, or change in existing therapy) or related to a GSK concomitant medication, will be recorded from the time a subject consents to participate in the study up to and including any follow up contact. All SAEs will be reported to GSK within 24 hours, as indicated in Section 6.3.8.

### 6.3.8. Method of Detecting AEs and SAEs

Care must be taken not to introduce bias when detecting AEs and/or SAEs. Open-ended and non-leading verbal questioning of the subject is the preferred method to inquire about AE occurrence. Appropriate questions include:

"How are you feeling?" or for paediatric studies, "How does your child seem to feel?"

"Have you had any (other) medical problems since your last visit/contact?" or for paediatric studies, "Has your child had any (other) medical problems or seem to act differently in any way since his/her last visit/contact?"

"Have you taken any new medicines, other than those provided in this study, since your last visit/contact?" or for paediatric studies, "Has your child needed to take any medicines, other than those provided in this study, since his/her last visit/contact?"

# 6.3.9. Prompt Reporting of Serious Adverse Events and Other Events to GlaxoSmithKline

Serious adverse events, pregnancies and liver function abnormalities meeting pre-defined criteria will be reported promptly by the Investigator to GlaxoSmithKline as described in the following table once the Investigator determines that the event meets the protocol definition for that event.

	Initial	Reports	Follow-up Information on a Previous Report			
Type of Event	Time Frame	Documents	Time Frame	Documents		
All SAEs	24 h	"SAE" data	24 h	Updated "SAE"		
		collection tool		data collection tool		
Pregnancy	2 Weeks	Pregnancy	2 Weeks	Pregnancy Follow-		
		Notification Form		up Form		
Adverse Drug	5 calendar	ADR	5 calendar days	ADR Follow-up		
Reaction	days	Form	-	Form		
(ADR)						

#### 6.3.9.1. Regulatory Reporting Requirements for SAEs

Prompt notification of SAEs by the investigator to GSK is essential so that legal obligations and ethical responsibilities towards the safety of subjects are met.

GSK has a legal responsibility to notify both the local regulatory authority and other regulatory agencies about the safety of a product under clinical investigation. GSK will comply with country specific regulatory requirements relating to safety reporting to the regulatory authority, Institutional Review Board (IRB)/Independent Ethics Committee (IEC) and investigators.

Investigator safety reports are prepared for suspected unexpected serious adverse reactions according to local regulatory requirements and GSK policy and are forwarded to investigators as necessary.

An investigator who receives an investigator safety report describing a SAE(s) or other specific safety information (e.g., summary or listing of SAEs) from GSK will file it with the IB and will notify the IRB/IEC, if appropriate according to local requirements.

## 6.3.10. Serum Creatinine Elevation

Serum creatinine values  $\ge 0.5 \text{ mg/dL}$  above baseline should be confirmed by repeat testing within 3 calendar days of receipt of results.

For serum creatinine elevations  $\geq 0.5 \text{ mg/dL}$  above baseline, subjects may continue all study medication, but it is recommended that subjects be monitored weekly until the serum creatinine returns to the original baseline value or  $\leq 0.3 \text{ mg/dL}$  from baseline.

All study drugs should be permanently discontinued in the event that repeat testing of serum creatinine confirms >2.0 mg/dL. The subject should be followed weekly until the serum creatinine reaches within 0.3 mg/dL of the baseline value.

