## 1.3. Benefit:Risk Assessment

Summaries of findings from both clinical and non-clinical studies conducted with TDF can be found in the Investigator's Brochure and China-specific prescribing information for TDF in CHB. The following section outlines the risk assessment and mitigation strategy for this protocol:

Potential Risk of Clinical Significance	Data/Rationale for Risk	Mitigation Strategy								
Investigational Product (IP)										
Renal toxicity	TDF is principally eliminated by the kidney. Renal impairment, including cases of acute renal failure and Fanconi syndrome (renal tubular injury with severe hypophosphatemia), has been reported with the use of VIREAD	
 
Exclusion of CHB patients with creatinine clearance <70 ml/min
 
Monitor renal function every 12 weeks
 
Dosing interval adjustment of VIREAD is recommended in all patients with creatinine clearance below 50 ml/min.
 
All study drugs should be permanently discontinued in the event that repeat testing
 
								

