#### Dose reduction in the patients with renal insufficiency

If subjects develop renal insufficiency (defined by serum creatinine clearance) during study treatment, the following dose reduction criteria should be used when subjects have a serum creatinine clearance of <50 ml/minute:

Calculated	Requiring Haemodialysis			
≥ 50	30-49	10–29		
TDF 300 mg every 24 h	TDF 300 mg every 48 h	TDF 300 mg every 72 h	TDF 300 mg every 7 days or after a total of approximately 12 h of dialysis b	
LAM tablets 100mg every 24h	Use	of LAM tablets is prohil	bited	
ETV tablets 0.5mg every 24h	ETV tablets 0.5mg every 48h	ETV tablets 0.5mg every 72h	ETV tablets 0.5mg every 5 to 7 days c	
LdT tablets 600mg every 24h	LdT tablets 600mg every 48h	LdT tablets 600mg every 72h	LdT tablets 600mg every 96h d	

a. Calculated using ideal (lean) body weight.

b. Generally once weekly assuming three haemodialysis sessions a week of approximately 4 h duration. Medication should be administered following completion of dialysis.

c. If administered on a hemodialysis day, administer ETV after the hemodialysis session.

d. When administered on hemodialysis days, administer LdT after hemodialysis.

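### For confirmed creatinine above 2.0 mg/dL with clearance below 50 ml/min, protocol 5.1.2 continues TDF at a longer interval while 6.3.10 stops it permanently, and neither rule is given priority

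*Protocol*

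**What the plan says.** Three places in the protocol govern what a site does when renal function falls.

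- **Section 5.1.2, dose reduction in renal insufficiency.** The trigger is clearance: "the following dose reduction criteria should be used when subjects have a serum creatinine clearance of <50 ml/minute". The table then keeps TDF going at 30–49 ml/min ("TDF 300 mg every 48 h"), at 10–29 ml/min ("TDF 300 mg every 72 h") and on haemodialysis ("TDF 300 mg every 7 days or after a total of approximately 12 h of dialysis"). It sets no serum creatinine limit and does not refer to 6.3.10.
- **Section 6.3.10, serum creatinine elevation.** The trigger is creatinine. For rises of at least 0.5 mg/dL over baseline, "subjects may continue all study medication, but it is recommended that subjects be monitored weekly". Above the higher threshold the rule is different: "All study drugs should be permanently discontinued in the event that repeat testing of serum creatinine confirms >2.0 mg/dL". There is no exception for a subject already on an adjusted interval, and no reference to 5.1.2.
- **Risk table in 1.3/1.3.1, renal toxicity row.** One bullet reads "Dosing interval adjustment of VIREAD is recommended in all patients with creatinine clearance below 50 ml/min". The next begins "All study drugs should be permanently discontinued in the event that repeat testing" and sets the same threshold of 2 mg/dL. Neither bullet is ranked above the other. The row refers the reader to 6.3.9, which is prompt reporting of serious adverse events; the creatinine rule is in 6.3.10.

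**The concern.** One rule is keyed to clearance and the other to serum creatinine, but clearance is calculated from creatinine, so one laboratory result can trigger both. When it does, one section says to continue at a longer interval and the other says to stop for good. Two sites could each follow the protocol and treat the same confirmed result in opposite ways.

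Renal toxicity is the first risk listed for the drug, so consistent handling matters for safety and for reading the renal safety data. There may also be an effect on the primary endpoint, since a subject taken off treatment and one kept on it may be classified differently at week 144.

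**Working it through.** The documents state no figure for this overlap, so there is nothing to reproduce. The check is whether the two triggers can be met together under the protocol's own formula.

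**Inputs from the protocol.** Appendix 1 gives CLcr = (140 − age) × weight / (72 × Scr), multiplied by 0.85 for women, using ideal body weight, or actual weight if lower. Ages run from 18 to 65 (4.2). Clearance below 70 ml/min is excluded at entry (4.3). The stop threshold is 2.0 mg/dL (6.3.10). The table cut-offs are 50, 30 and 10 ml/min (5.1.2).

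**Assumptions.** The ages and weights below are illustrative; the documents give no expected distribution.

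**Step 1: clearance at 2.0 mg/dL, and creatinine at each cut-off.** Let k = (140 − age) × weight × (0.85 if female) / 72. Clearance at 2.0 mg/dL is then k/2.0, and the creatinine at a given clearance is k/CLcr. For the man of 40 y and 65 kg, k = 100 × 65 / 72 = 90.3, so clearance at 2.0 mg/dL is 45.1 and clearance of 30 corresponds to 90.3/30 = 3.01 mg/dL.

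| Subject | CLcr at 2.0 mg/dL | Scr at CLcr 50 | Scr at CLcr 30 | Scr at CLcr 10 |
|---|---|---|---|---|
| Man, 25 y, 70 kg | 55.9 | 2.24 | 3.73 | 11.2 |
| Man, 40 y, 65 kg | 45.1 | 1.81 | 3.01 | 9.0 |
| Man, 65 y, 60 kg | 31.3 | 1.25 | 2.08 | 6.3 |
| Woman, 40 y, 52 kg | 30.7 | 1.23 | 2.05 | 6.1 |
| Woman, 65 y, 45.5 kg | 20.1 | 0.81 | 1.34 | 4.0 |

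**Step 2: where the rules collide.** Take the man of 40 y and 65 kg.

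- Confirmed 2.5 mg/dL: clearance 90.3/2.5 = 36.1. The table gives the 30–49 interval; 6.3.10 says stop permanently.
- Confirmed 3.5 mg/dL: clearance 90.3/3.5 = 25.8. The table gives the 10–29 interval; 6.3.10 again says stop.

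For all three men the whole 10–29 column lies above 2.0 mg/dL. For every subject shown, the lower part of that column does, because clearance of 10 needs at least 4.0 mg/dL.

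**Step 3: where they do not collide.**

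- The woman of 65 y and 45.5 kg can use the whole 30–49 column (0.81 to 1.34 mg/dL) and the 10–29 column down to 20.1 ml/min before reaching 2.0 mg/dL.
- The man of 65 y and the woman of 40 y can use nearly all of the 30–49 column.
- The man of 40 y can use only its top, from 1.81 to 2.0 mg/dL (clearance about 50 down to 45.1).
- A man of 65 y has clearance below 30 at 2.0 mg/dL only if his weight is under 30 × 144/75 = 57.6 kg.

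**Step 4: sensitivity to body size.** With ideal weights for assumed heights of 160–190 cm in men and 150–170 cm in women, and ages 18–65, clearance at 2.0 mg/dL is 29.6–71.2 ml/min in men and 19.2–44.2 in women. For men of 165–180 cm, clearance of 30 is reached at 2.13–4.24 mg/dL, always above the stop threshold. The conclusion does not depend on the five examples.

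**Step 5: would the planned output show it?** SAP 7.5.3 counts clearance below 50 ml/min and confirmed creatinine rises of 0.5 mg/dL. It does not count creatinine above 2.0 mg/dL. In SAP 8.2 values above 2.0 and up to 3.0 mg/dL are Grade 2, and the graded summary covers Grades 3 and 4 only. SAP 7.5.1 would show adverse events leading to discontinuation, dose change or interruption, but not who met the stop rule.

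**The case against.** The best defence is that the two rules form a ladder: lengthen the interval as clearance falls, and stop if creatinine is confirmed above 2.0 mg/dL. The risk table lists them in that order, the stop is unconditional, and it needs a repeat test, so the table can govern until confirmation. This reading is plausible, but no sentence states it. It would also leave much of the 10–29 column without use. The haemodialysis column would go the same way if, as one would infer though the documents do not say it, such subjects exceed 2.0 mg/dL.

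Three stronger readings are tempting, and the documents do not support them.

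- **That every subject on the table gets opposite instructions.** Step 3 shows otherwise. Where creatinine is 2.0 mg/dL or less, the table operates alone.
- **That a younger, larger man at clearance 50 or more is told to continue by the table and to stop by 6.3.10.** The reduction criteria are triggered only below 50. The column for 50 and above shows the ordinary dose and does not override 6.3.10, so only the stop rule applies.
- **That a stopped subject automatically fails the primary endpoint.** The risk table says subjects withdrawn from the product are followed on the original schedule, and SAP 7.5.1 separates stopping the drug from leaving the study. Against that, protocol 4.4 requires withdrawal from the study after an interruption of 28 days or more, 8.3.5 counts non-completers as failures, and SAP 6.2 fails a discontinued subject without saying whether this means drug or study. The texts lean towards failure but do not settle it.

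It is also fair to say that entry at clearance of at least 70 ml/min makes these events uncommon, and that the documents give no expected rate.

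**Conclusion.** The contradiction stands for subjects with confirmed creatinine above 2.0 mg/dL and clearance below 50 ml/min, and only for them. In that region 5.1.2 and 6.3.10 cannot both be followed, and nothing in the protocol says which prevails. The wrong cross-reference in the risk table makes the answer harder to find.

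The number of subjects is probably small. If stopping or continuing did change a subject's outcome, each one would move the primary proportion by 1/200 = 0.5 percentage points at the planned enrolment. The case for a change therefore rests on consistent renal safety management, not on the endpoint. The overlap rests on the protocol's own formula and on assumed ages, weights and heights; these move its boundary but do not remove it. No view is taken on which rule is clinically right.

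**What to change.** - **Protocol.** The clinical team should reconcile the risk table in 1.3/1.3.1, section 5.1.2 and section 6.3.10, and state in each which rule applies when both triggers are met. The risk table's reference to 6.3.9 should point to 6.3.10.
- **SAP 7.5.3.** Add the number and percentage of subjects with confirmed creatinine above 2.0 mg/dL, beside the planned count of clearance below 50 ml/min. Define confirmation for this count by the repeat test that 6.3.10 requires; the SAP's two-consecutive-visits definition is written for the 0.5 mg/dL rise.
- **SAP 6.2.** State whether a discontinued subject means one who stops the drug or one who leaves the study, so that the week 144 classification of a subject stopped under 6.3.10 is fixed in advance.

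The cost is a protocol clarification, one extra row in a safety table and one sentence on the endpoint. No new data are needed, since creatinine clearance is already assessed every 12 weeks.

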## 6.3.11. Other Safety Outcomes

#### Laboratory Assessments

All protocol required laboratory assessments, as defined in Table 1, must be performed by the central laboratory, [Guangzhou Tigermed Research Institution Co., Ltd]. Laboratory assessments must be conducted in accordance with the Central Laboratory Manual and Protocol Time and Events Schedule. Laboratory requisition forms must be completed and samples must be clearly labelled with the subject number, protocol number, site/centre number, and visit date. Details for the preparation and shipment of samples will be provided by [Guangzhou Tigermed Research Institution Co., Ltd]. Reference ranges for all safety parameters will be provided to the site by [Guangzhou Tigermed Research Institution Co., Ltd].

If additional non-protocol specified laboratory assessments are performed at the institution's local laboratory and result in a change in patient management or are considered clinically significant by the investigator (e.g., SAE or AE or dose modification) the results must be recorded in the subject's CRF. Refer to the SPM for appropriate processing and handling of samples to avoid duplicate and/or additional blood draws.

# 7. DATA MANAGEMENT

For this study subject data will be collected using GlaxoSmithKline defined CRFs and combined with data provided from other sources in a validated data system.

Management of clinical data will be performed in accordance with applicable GlaxoSmithKline standards and data cleaning procedures to ensure the integrity of the data, e.g., removing errors and inconsistencies in the data. Adverse events and concomitant medications terms will be coded using MedDRA and an internal validated medication dictionary, GSK Drug. [An appropriate medical dictionary that covers all approved drugs in the region will be referenced.] Original CRFs will be retained by GlaxoSmithKline, while the Investigator will retain a copy. In all cases, subject initials will not be collected or transmitted to GlaxoSmithKline, according to GlaxoSmithKline policy.

# 8. DATA ANALYSIS AND STATISTICAL CONSIDERATIONS

## 8.1. Hypotheses

No hypothesis is tested in this study.

## 8.2. Study Design Considerations

## 8.2.1. Sample Size Assumptions

Sample sizes are chosen based on feasibility and precision because no hypothesis is tested in this study.

The primary endpoint is the proportion of subjects with serum HBV DNA <20 IU/ml of TDF in multiple NAs treatment failure patients at Week 144.

To decide the number of subjects for analysis, some precision calculations have been performed. From our historical data, we hypothesize that the proportion of subjects with serum HBV DNA <20 IU/ml in multiple NAs treatment failure patients treated with TDF at Week 144 was 80%. A sample size of 170 patients will allow us to estimate the confidence interval of the incidence with a margin of error at  $\pm$  6% (range from 74-86%). Assuming a dropout rate of 15 per cent during a 144 week period, the number of patients required overall is estimated to be 200.

Formulae for the sample size estimation.

As Margin of error is: 
$$E = z_c \sqrt{\frac{p(1-p)}{n}}$$

So, the sample size required is:  $N = p(1-p) \left(\frac{z_c}{e}\right)^2$ 

## 8.2.2. Sample Size Sensitivity

The sample size estimate is sensitive to the assumed proportions and the margin of error. The estimated sample size for several scenarios is presented in Table 2.

### Table 2 Sample Size Sensitivity Table

Assumed	Margin of	95% confidence	
proportion	error	interval	Sample Size
75%	5%	(70%,80%)	288
75%	6%	(69%,81%)	200
75%	7%	(68%,82%)	147
80%	5%	(75%,85%)	246
80%	6%	(74%,86%)	170

80%	7%	(73%,87%)	125
85%	5%	(80%,90%)	196
85%	6%	(79%,91%)	136
85%	7%	(78%,92%)	100

#### 8.2.3. Sample Size Re-estimation

No sample size re-estimation is planned.

## 8.3. Data Analysis Considerations

#### 8.3.1. Analysis Populations

Three populations will be used in the analysis:

• modified Intent to Treat(mITT) Population

The mITT population is defined as all recruited subjects who receive at least one dose of study medication.

• Per Protocol (PP) population

The PP population will consist of subjects in the mITT population with the exception of major protocol violators.

• Safety Analysis (SA) population

The SA population is defined as all subjects who receive at least one dose of study medication and have at least one post baseline safety assessment.

All efficacy endpoints will be analysed using the mITT and PP population.

All safety endpoints will be analysed using the SA population according to the actual treatment they received.

### 8.3.2. Analysis Data Sets

For information on the analysis data sets please refer to the RAP.

#### 8.3.3. Treatment Comparisons

It is a single arm study and no comparison will be performed.

#### 8.3.4. Interim Analysis

No interim analysis is planned for this study.

## 8.3.5. Key Elements of Analysis Plan

Missing data can have an impact upon the interpretation of the trial data. In general, values for missing data will not be imputed unless otherwise specified.

All serum HBV DNA results below the lower limit of detection will be analysed as being the value of the lower limit of detection.

For the primary analysis of HBV DNA<20IU /ml at Week 144, data from non-completers will be considered to be "failures".

#### 8.3.5.1. Efficacy analyses

In this study, data will be summarised as mean, medium, standard deviation, maximum, and minimum for continuous variables, and in tables of frequencies and percentages for categorical variables.

For the primary endpoint, descriptive analysis will be used to evaluate the efficacy of TDF in multiple NAs treatment failure patients.

Multiple-factor analysis will be used to assess the baseline variables that were significantly associated with HBV DNA negativity at week 144.

The detail of primary, secondary and other efficacy endpoint analysis will be included in the RAP.

#### 8.3.5.2. Safety analyses

Clinical safety observations will include: extent of exposure information, AEs, deaths, laboratory abnormalities and withdrawals from study.

Extent of exposure to study drug data will be generated from the study drug administration page of CRF. Exposure data will be summarised by treatment group.

Adverse events will be assigned preferred terms and categorized into body systems according to the MedDRA classification of the World Health Organisation terminology. The proportion of subjects who experienced AEs will be calculated by dividing the number of subjects who experienced the AE during the treatment period by the number of subjects evaluable for safety analysis. Adverse events will be summarised by treatment group, and by body system and event within each body system. The following summaries of AEs will be provided:

- All AEs.
- All treatment related AEs.
- All SAEs.
- All treatment related SAEs.
- All AEs leading to permanent discontinuation of study drug.
- All AEs leading to permanent discontinuation from the study.

• All AEs that caused a change in dose or temporary interruption of study drug.

